8.4. WITHDRAWAL OF INDIVIDUAL SUBJECTS

Participants can leave the study at any time for any reason if they wish to do so without any consequences. The investigator can decide to withdraw a participant from the study for urgent medical reasons, e.g. imminent suicide risk. Since only individuals with imminent suicide risk will be excluded, those with suicidal thoughts at inclusion/screening will be followed up by the helpers. When during calls with DWM/PM+ helpers, participants show deterioration with imminent suicidal plans than the helper will discuss this immediately with one of the DWM/PM+ supervising mental health specialists. Also, when there is clear suspicion of worsening of (severe) mental health problems, participants will be asked to withdraw from the study and contact their general practitioner for a referral to specialized mental health treatment.

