8.2. RANDOMIZATION, BLINDING AND TREATMENT ALLOCATION

After the screening and the baseline assessment, participants will be randomized to either the treatment group (n=105) or the comparison group (n=105), with an equal probability of assignment to each group (allocation ratio 1:1). The trial is a single-blind RCT (i.e. outcome assessors are blind to treatment allocation). Randomization will be carried out through computerized software (e.g. Castor) using limited block size (e.g. 6-12 participants per block) and will be performed by an independent person who is not involved in the assessment of participants. If participants are randomized into the treatment group, they will be allocated to a DWM helper. This is also done blind by an independent person who is not involved in the assessment. The allocated helper will send an e-mail to the participant to set up a time and date for a first acquaintance telephone call before the intervention starts. During this call, the weekly support calls of the DWM helper will be discussed and planned. If participants still meet the inclusion criteria 2 weeks after the DWM program ended, they will be contacted by the PM+ helper (might be the same helper as for DWM) to plan five consecutive (tele-conferencing) meetings of 60 minutes with the participant. The first session will be scheduled within a few days and not longer than one week after the pre-intervention assessment.

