8.5. REPLACEMENT OF INDIVIDUAL SUBJECTS AFTER WITHDRAWAL

No new subjects will be included for each withdrawn subject. In our power calculation for the sample size, we have taken into account 30% attrition.

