8.6. FOLLOW-UP OF SUBJECTS WITHDRAWN FROM TREATMENT

If a subject decides to withdraw from the study, the investigator will ask for the reason. It will be enquired whether the subject wishes to withdraw from the study or from a specific time point only and so whether the subject can be re-contacted at a later time. Withdrawal from the study will have no effect on the regular treatment. Subjects who leave the study for medical reasons will be followed until the interfering condition has resolved or reached a stable state.

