9.3 FOLLOW-UP OF ADVERSE EVENTS

All AEs will be followed until they have abated, or until a stable situation has been reached.

Depending on the event, follow-up may require additional tests or medical procedures as indicated, and/or referral to the general physician or a medical specialist. SAEs need to be reported till end of study. The DWM and PM+ helpers will be supervised and receive weekly supervision by experienced mental health care professionals. If, during the course of the study, participants in the treatment group (PM+/DWM/CAU) or comparison group (CAU only) show severe psychiatric symptoms (e.g., psychosis, imminent suicide risk, etc.), or any other symptoms occur that require immediate specialist treatment and follow-up, they will be referred to specialist staff (e.g. psychiatrists) for immediate follow-up. The researcher from UNIVERSITY OF VERONA will be responsible to monitor this process and make sure the appointment has been made.

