10.1 PRIMARY OUTCOME(S)

The statistical analysis of the RCT will estimate effectiveness of the stepped-care DWM/PM+ with PFA and CAU intervention compared to PFA and enhanced CAU alone, with PHQ-ADS score as the primary study outcome.

The primary outcome will be summarized using number of subjects (n), minimum and maximum; and means, standard deviations (SD) for normally distributed data, or medians and inter-quartile ranges for non-normally distributed data. To measure comparisons at baseline between the two treatment groups t -tests (continuous variables) or chi-squared test (categorical variables) will be conducted for normally distributed data; Mann-Whitney tests will be conducted for continuous non-normally distributed data.

Both intention-to-treat (ITT) analysis, including all randomized participants ($n=212$), and completers' (per protocol - PP) analysis will be carried out. The main conclusion of the trial will be based on the ITT analysis of the primary outcome. A secondary analysis of the primary outcome will also be presented using the PP population.

The statistical analysis will be masked, i.e. the trial statistician will be blinded to the treatment groups until the analysis has been completed. Moreover, the trial statistician will not be involved in determining participants' eligibility, in administering the intervention, in measuring the outcomes or in entering data.

To estimate the treatment effect, a linear mixed model will be employed for the primary endpoint analysis, which will have treatment as fixed effects, baseline measurement of primary endpoint as covariate, and subject as random effects. The mean difference between two treatment arms at each visit/time together with its 95% confidence interval will be derived from the mixed model. Covariate-adjusted mixed model of primary endpoint will also be performed by adding pre-specified covariates at baseline (gender, age, education, prior trauma, COVID-19 related events and stressor list) into the above model.

Missing data

Missing data will be treated as missing at random (MAR). No imputations of missing values will be made, as multilevel models can deal with missing data (Singer, Willett & Willett, 2003).

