11.4 BENEFITS AND RISKS ASSESSMENT, GROUP RELATEDNESS

Participants randomized into the DWM/PM+ treatment group may benefit from their participation in terms of expected reductions in psychological distress. The risks associated with participation are estimated to be minimal, since DWM and PM+ have shown to reduce psychological distress in previous studies (Purgato et al., 2019; Tol et al., 2020; Bryant et al., 2017; Rahman et al., 2016b). Participants in both the treatment and comparison group will not be withheld care as usual (note: the treatment group receives CAU along with stepped-care DWM/PM+ and psychological first aid (PFA), the comparison group will receive enhanced CAU and PFA only).

It is possible that participants experience (increased) stress/depressive feelings during the PM+ sessions (e.g. by speaking of stressful events happening at work or speaking of their personal (living) situation). The intervention will be supervised and strictly monitored by experienced clinical psychologists. If a participant deteriorates during the intervention period, or has elevated symptoms at follow-up assessments, (s)he will be advised to contact his/her general practitioner (part of the CAU), who may refer the participant for continued or high-intensity treatment, e.g. referral to an external specialist (licensed psychologist or psychiatrist). Whether referral has taken place, will be actively followed up by the researchers.

Participants may also experience some distress during the assessments, as they may think of their situation. These assessments will be conducted online through self-reporting, and/or through video-calling. The interviewer-administered assessments will be administered by assessors who are trained and closely monitored by the University of Verona research team. Administering the instruments is crucial to draw conclusions about the feasibility and credibility of the intervention. In case of an undesirable emotional reaction both during the intervention as well as during the follow-up assessments the researcher or a clinician will be available to provide support if necessary or desirable.

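### Section 8.4 asks participants who clearly worsen to leave the study, not only the intervention, and 8.6 does not secure their later PHQ-ADS, so loss of the primary outcome can depend on deterioration not yet recorded

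*Protocol*

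**What the plan says.** Protocol section 8.4 sets a trigger and a consequence: "when there is clear suspicion of worsening of (severe) mental health problems, participants will be asked to withdraw from the study", with a referral through the general practitioner. The sentence is not limited to one arm and does not separate stopping the intervention from leaving the trial. Section 8.4.1, directly below, states that specific withdrawal criteria do not apply.

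Section 8.6 is headed as follow-up after withdrawal from treatment, but its text concerns leaving the study. The reason is asked, and "It will be enquired whether the subject wishes to withdraw from the study or from a specific time point only", together with whether later contact is allowed. It adds that "Subjects who leave the study for medical reasons will be followed until the interfering condition has resolved or reached a stable state". No outcome measure or visit is named.

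Two other sections deal with participants who get worse. Section 9.3 provides specialist referral when "participants in the treatment group (PM+/DWM/CAU) or comparison group (CAU only) show severe psychiatric symptoms". Section 11.4 begins "If a participant deteriorates during the intervention period, or has elevated symptoms at follow-up assessments" and goes on to advise contact with the general practitioner. Neither mentions withdrawal, and neither says whether assessment continues.

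On analysis, section 10.1 states that "The main conclusion of the trial will be based on the ITT analysis of the primary outcome", with all 212 randomised participants included, missing data taken as missing at random, no imputation, and baseline PHQ-ADS as a covariate. On losses, section 8.5 says that withdrawn participants are not replaced and that "In our power calculation for the sample size, we have taken into account 30% attrition".

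**The concern.** The protocol itself prompts this exit, and its trigger lies close to what PHQ-ADS measures. If the worsening already shows in a recorded post-baseline PHQ-ADS, a likelihood-based mixed model under missing at random can handle the later gaps. If it was noticed on a call and the person leaves before the next assessment, the data the model uses do not contain the reason for leaving, and the assumption fails.

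There is room for this. DWM takes five weeks (section 7.1) and T2 comes two weeks after it (section 8.1), so about seven weeks pass from the start of DWM without a scheduled PHQ-ADS. Someone who leaves in that window has only a baseline value. Because baseline enters as a covariate, that person contributes no outcome to the ITT analysis.

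The arms may also differ in how often worsening is noticed. Section 8.2 says "If participants are randomized into the treatment group, they will be allocated to a DWM helper", and the weekly helper calls and PM+ sessions exist only in that arm. More exits there would favour the intervention. If controls worsen more, the same rule removes more of them and works against the intervention. The documents do not say which will happen. Values that were never collected cannot be recovered by a later SAP.

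**Working it through.** **The plan's own allowance.** From section 6.4, 74 per group with 30% attrition gives 74/(1 − 0.30) = 105.7, so 106 per group and 212 in total. This reproduces. It allows for about 0.30 × 106 ≈ 32 losses per arm. It protects the number analysed and says nothing about who is lost.

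**Inputs for the size of the bias.** Correlation ρ = 0.9 (section 6.4) and target d = 0.3 (section 8.1.1). Assumed, because the documents give no figure: ρ = 0.7 as an alternative, and a lost share q of 2%, 5% or 10% (about 2, 5 or 11 of 106). PHQ-ADS is standardised to SD 1.

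**Upper bound: the worst share q leaves one arm before T2.** Given baseline, T4 has residual SD √(1 − ρ²), which is 0.436 at ρ = 0.9 and 0.714 at ρ = 0.7. Removing the worst share q of a normal distribution moves the mean of the rest by φ(z₁₋q)/(1 − q). The bound is the product of the two.

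| q | φ(z)/(1 − q) | ρ = 0.9 | ρ = 0.7 |
|---|---|---|---|
| 2% | 0.0484/0.98 = 0.0494 | 0.022 | 0.035 |
| 5% | 0.1031/0.95 = 0.1086 | 0.047 | 0.078 |
| 10% | 0.1755/0.90 = 0.1950 | 0.085 | 0.139 |

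A large simulation with regression on baseline agrees with these values to within about 0.001.

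**Losses in both arms.** Subtract the two factors:

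- 5% against 2%: (0.1086 − 0.0494) × 0.436 = 0.026 at ρ = 0.9, and 0.042 at ρ = 0.7.
- 10% against 5%: (0.1950 − 0.1086) × 0.436 = 0.038, and 0.062 at ρ = 0.7.
- Equal shares of the worst in each arm give 0.

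The sign favours the intervention if the treatment arm loses more, and goes against it if the control arm does.

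**Milder case: selection on change from baseline to an unrecorded T2.** With equal correlation between visits, the factor √(1 − ρ²) is replaced by ρ(1 − ρ)/√(2(1 − ρ)).

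- ρ = 0.9: 0.09/0.447 = 0.201, so the bias is 0.010, 0.022 and 0.039 for q = 2%, 5% and 10%.
- ρ = 0.7: 0.21/0.775 = 0.271, so the bias is 0.013, 0.029 and 0.053.

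**Does recording matter?** A separate simulation took a true effect of −0.30 and let a share of the worst-changing fifth leave at each visit.

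- Leaving after the worse score was recorded: estimates of −0.298 to −0.303, so essentially no bias.
- Leaving before it was recorded, 30% share in the treatment arm only: −0.33 at ρ = 0.9 and −0.37 at ρ = 0.5.
- The same, 10% share: −0.31 and −0.32.
- A 30% share in both arms: −0.28 at either correlation. Because the intervention works in this model, more controls cross the threshold (15.8% lost against 8.4% at ρ = 0.9). A rule applied equally can therefore also bias the estimate, here against the intervention.

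**The case against.** The strongest reply is that section 8.6 is not silent. In this protocol the time points are the assessments (section 8.1), so asking whether someone is leaving only one time point, and whether they may be contacted again, opens a route to later PHQ-ADS, including T4. This stands in part: such an enquiry could save some assessments. But it is an enquiry and not a commitment, and it is written for a subject who decides to leave, not for one whom the protocol has asked to leave. The repeated calls in section 8.3 are for people who miss an assessment, not for people who have withdrawn.

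Sections 9.3 and 11.4 can be read as compatible with 8.4, and 8.4.1 suggests that no formal removal rule was meant. That is fair, but none of them says whether such a participant stays in assessment. That is the gap.

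The size is also open to challenge. The trigger is narrow, since section 6.3 excludes severe mental disorder and imminent suicide risk at entry. The larger figures are ceilings. PM+ starts only after T2, so worsening seen during PM+ normally follows at least one recorded post-baseline score. Unequal detection between the arms is an inference, not something the protocol states. All of this stands. It limits the severity but does not remove the defect.

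**Conclusion.** The concern holds. As written, the protocol asks participants who clearly worsen to leave the study and secures no T2–T4 PHQ-ADS from them, while the main analysis assumes that missingness does not depend on unrecorded outcomes.

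The likely size is modest. One-arm loss of 2% to 10% gives at most 0.02 to 0.09 SD at ρ = 0.9 and 0.04 to 0.14 SD at ρ = 0.7. Under selection on change it is about 0.01 to 0.04 SD and 0.01 to 0.05 SD. The target is 0.3. These figures rest on assumed loss shares, normality and, for 0.7, an assumed correlation. The direction is unknown, and the bias is near zero if worsening is recorded before exit or if equal shares of the worst are lost. It is a change that should be made, not a fatal flaw. Confidence is medium, because the number affected cannot be known from the protocol.

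**What to change.** Reconcile sections 8.4, 8.6, 9.3 and 11.4 on what happens to a randomised participant who worsens, with the clinical handling left to the sponsor. In 8.4 and 8.6, separate stopping the intervention from leaving the study, and state three things:

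- Stopping the intervention or being referred does not by itself end T2–T4 outcome assessment, in either arm.
- Such participants are invited to continue assessments for as long as they consent.
- Worsening is recorded as a reason for stopping, with its date.

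A sensitivity analysis for participants lost after recorded worsening is optional and can sit in the SAP. The cost is a few sentences and some extra effort to follow participants who have been referred. The sample size does not change.

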We will assess DWM protocol adherence at post-intervention based on meta-data collected during the intervention (i.e. by tracking participants usage of the DWM app such as who accesses what page, how often, how much time participants spend on the app etc.). We will only use this meta-data during the intervention to remind each participant (e.g. through e-mail) after finishing each module to let them know that they should start a new module. Additionally, participants receive a weekly phone call from a helper to see how they are doing and to check on their progress.

Step 2: Problem Management Plus (PM+)

PM+ is a new, brief, psychological intervention program based on cognitive behavioral therapy (CBT) techniques that are empirically supported and formally recommended by the WHO (Dua et al., 2011). The manual involves the following empirically supported elements: problem solving plus stress management, behavioral activation, facing fears, and accessing social support. Figure 2 shows a brief outline of the five sessions. In these 60-minute sessions participants may talk to trained non-professional helpers (who are supervised by registered (clinical) psychologists). We will follow this outline, except that we excluded all assessment instruments from the manual, since they are administered at the assessments instead of at the intervention sessions. PM+ has four core features: it is brief (five sessions); delivered by para-professionals; transdiagnostic thereby addressing depression, anxiety, PTSD, stress and problems as defined by people themselves; originally designed for people in low-income country communities but easily adaptable to different (vulnerable) populations, cultures and languages.

In this study, the delivery mode of the PM+ intervention will be flexible, with remote delivery in phases of the pandemic when physical distancing rules apply. The PM+ intervention has been culturally and contextually adapted. This is a future-oriented attempt towards a more holistic mental health care system that can flexibly switch between modes of delivery (e.g. remotely (e.g. Zoom) or face-to-face), depending on the needs and the specific containment measures

that apply, and the specific preferences and needs of the participant.

Protocol adherence

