Suicidality will be explored at several time-points (at T0, at T1, during PM+ and at follow-up assessments) with either the ‘assessment of thoughts of suicide’ risk tool (from PM+; WHO, 2016, pp. 86) when assessed in face-to-face contact (e.g. in person or remotely through teleconferencing or telephone) or with the self-administered step-by-step suicidality question (Van ‘t Hof et al., 2021) when assessed with an online questionnaire. People who have plans to end their life (as indicated by an answer of “yes” on the screening question - “In the past week/month, have you had serious thoughts or a plan to end your life?”) will be excluded from the study. Participants who answer “yes” to this additional screening question will be considered at imminent risk of suicide (Van ‘t Hof et al., 2021). In case of imminent suicidal risk, people are excluded from participation. They will be explained (on-screen or by telephone/teleconferencing or in person) that they cannot participate but that they may need additional mental health support with advice to go to an emergency room or to a local psychiatric center (all the details on the available local mental health services will be provided). They will also be presented with suggestions for steps to follow in order to receive mental health care (e.g. contact general practitioner), encouraged to seek help, and provided with additional self-care tips.

Severe mental disorder

(Suspicion of) a severe mental disorder will be assessed by the PM+ tool ‘Impairments possibly due to severe mental, neurological or substance use disorders’. This is a tool which is to be filled in by the assessor based on their observations and judgment of the client’s behaviors. No questions are asked to the participant. The tool asks 4 questions related to the participant’s behavior: 1) does the client understand you (even though they speak the same language or dialect)?; 2) Is the client able to follow what is happening in the assessment to a reasonable extent?; 3) Are the client’s responses bizarre and/or highly unusual?; 4) From the client’s responses and behaviors, does it appear that they are not in touch with reality or what is happening in the assessment? If the answer is no to question 1 or 2, or yes

to question 3 or 4, the participant will be excluded.

Primary outcome measure

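### Section 8.4 asks worsening participants to leave the study, so the worst T4 scores can go missing, probably more often in the treated arm, under a MAR primary analysis with no imputation

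*Protocol*

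**What the plan says.** Section 8.4 first gives participants the right to leave at any time and lets the investigator withdraw someone for urgent medical reasons such as imminent suicide risk. It then adds a separate instruction: "when there is clear suspicion of worsening of (severe) mental health problems, participants will be asked to withdraw from the study". They are also told to see their general practitioner.

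Section 8.6 covers what follows. If the subject decides to withdraw, staff ask for the reason and whether re-contact is possible. For medical exits, "Subjects who leave the study for medical reasons will be followed until the interfering condition has resolved or reached a stable state". Neither provision requires PHQ-ADS at T2, T3 or T4.

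Two other sections deal with overlapping states and do not mention leaving the study. For severe symptoms in either arm, Section 9.3 says "they will be referred to specialist staff (e.g. psychiatrists) for immediate follow-up". Section 11.4 says: "If a participant deteriorates during the intervention period, or has elevated symptoms at follow-up assessments, (s)he will be advised to contact his/her general practitioner".

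On analysis, Section 10.1 states: "The main conclusion of the trial will be based on the ITT analysis of the primary outcome". It also states: "Missing data will be treated as missing at random (MAR). No imputations of missing values will be made".

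On contact, Section 7.1 says of DWM that "participants receive a weekly phone call from a helper to see how they are doing and to check on their progress". Those stepped up then have five PM+ sessions. Section 8.3 adds: "Suicidality will be explored at several time-points (at T0, at T1, during PM+ and at follow-up assessments"). The comparison arm has one PFA conversation, usual care and the scheduled assessments.

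**The concern.** The rule removes people from outcome collection because of a state closely related to the primary outcome. Three features make this harmful.

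- **The analysis cannot see the reason.** Worsening picked up in a call between assessments is in no recorded PHQ-ADS score. A mixed model predicts the missing T4 from the scores it has, and these look better than the participant now is. Someone who leaves before T2 has only the baseline covariate and adds nothing to the model, so the analysis no longer covers all 212 randomised.
- **Detection differs by arm.** Up to ten between-visit contacts (five DWM calls and five PM+ sessions) exist only in the treated arm. Controls are seen mainly at assessments, where PHQ-ADS is recorded as well.
- **The handling is inconsistent.** One participant could be withdrawn under Section 8.4, or only referred under Sections 9.3 or 11.4, with different effects on the primary data.

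If more worsening participants leave the treated arm, its T4 mean looks too good and the contrast is biased towards the intervention. Their cost data (CSRI) and the scheduled suicide-risk questions are lost too.

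**Working it through.** **The plan's own figure.** Section 6.4 gives 74 per group (power 0.95, two-sided alpha 0.05, Delta 0.3, rho 0.9) and 212 after 30% attrition. Reading Delta as the root of a variance ratio, a 1-df F test with noncentrality N × 0.3² has power 0.9496 at 73 per group and 0.9521 at 74. Then 74 / 0.70 = 105.7, so 106 per arm and 212 in total. The figure reproduces and is not in dispute. The 30% allowance protects precision, not against bias.

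**Assumed inputs.** The protocol gives no rate of withdrawal for worsening, overall or by arm. I use 5 treated v 1 control and 11 v 2, of 106 per arm, and vary the correlation around the protocol's 0.9.

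**Step 1: a bound by hand.** Suppose nothing recorded after baseline helps, and the fraction p with the largest rise from baseline to T4 is lost from the treated arm only. In SD units, the shift in the baseline-adjusted treated mean is, to first order,

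shift = −[(1 − ρ²) / √(2(1 − ρ))] × φ(z) / (1 − p), where z is the (1 − p) normal quantile.

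For p = 0.05, φ(z)/(1 − p) = 0.1086; for p = 0.10 it is 0.195.

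| ρ | First factor | p = 0.05 | p = 0.10 |
|---|---|---|---|
| 0.9 | 0.19/√0.2 = 0.425 | −0.046 | −0.083 |
| 0.5 | 0.75/1 = 0.75 | −0.081 | −0.146 |

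Simulated ANCOVA (1,000,000 participants per scenario) gives −0.048 and −0.083 at ρ = 0.9, and −0.085 and −0.154 at ρ = 0.5. Losing 5% from both arms gives zero to within 0.002. These figures lie towards the upper end because no T2 or T3 score is used.

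**Step 2: the planned type of model.** Baseline and T2 to T4 have SD 1 and common correlation ρ. Ordinary attrition is 25%, unrelated to outcome, so total loss is near 30%. Triggered participants keep T2 and lose T3 and T4. They are either the k largest worsenings (mean of T3 and T4 minus baseline) or k drawn at random from the worst 3k, which gives the two ends of each range. The analysis is a random-intercept model with visit, arm by visit and baseline; the true effect is 0, with 3,000 runs per cell.

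| ρ | Shift, 5 v 1 | Shift, 11 v 2 |
|---|---|---|
| 0.5 | −0.026 to −0.040 | −0.043 to −0.075 |
| 0.7 | −0.022 to −0.038 | −0.037 to −0.062 |
| 0.9 | −0.015 to −0.021 | −0.024 to −0.042 |

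As a share of a 0.3 SD effect at ρ = 0.9, this is 0.015/0.3 = 5% to 0.042/0.3 = 14%. A separate large-sample run gave about 0.014 to 0.039 SD at ρ = 0.9, 0.030 to 0.078 at ρ = 0.5, and about 0 with equal shares.

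**Step 3: error rates with no true effect.** The chance of a significant result favouring treatment is 2.2 to 2.6% without triggered exits, 3.8 to 6.1% with 5 v 1, and 4.8 to 8.9% with 11 v 2 (Monte Carlo SE about 0.3 to 0.5 points). For the two-sided test, take SE = √(2/75) × √(1 − ρ²), with about 75 analysed per arm. This gives roughly 5.4 to 6.2% (5 v 1) and 6.1 to 9.1% (11 v 2), against 5%.

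**Step 4: other patterns.** If worsening affects T3 only, the shift is 0.006 to 0.014 SD for 5% v 1% and 0.010 to 0.030 SD for 10% v 2%. Reversing the shares (1% treated v 5% control) gives 0.005 to 0.014 SD against treatment.

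**The case against.** **The imbalance is inferred.** The sentence in 8.4 names no arm. Suicide-risk questions at T2 to T4 apply to everyone, Section 9.3 covers both arms, and the helpers whom 8.4 charges with following up suicidal thoughts could include PFA helpers. Controls might also worsen more often. This stands as a limit: direction is probable, not certain. But detection between visits, where the recorded scores cannot reflect it, runs through contacts that only the treated arm has.

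**The rule is soft.** Participants are asked and may decline, Section 8.4.1 lists no specific withdrawal criteria, and someone who agrees to leave may fall under the re-contact question in 8.6. That would reduce the loss. It does not secure a T4 score.

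**The size rests on invented rates.** This is correct. The simulation also selects on future scores that staff could not know. And 0.3 is called Cohen's d in Section 8.1.1, while 74 per group reproduces only on the variance-ratio reading (d of about 0.6), on which the shares above halve.

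**MAR is an ordinary primary assumption, and sensitivity analyses belong in the SAP.** This is also correct, and MAR is not the fault here. Worsening already recorded at T2 or T3 is partly handled by the model. But no SAP can recover scores that the protocol's own rule stops staff from collecting.

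**Sections 9.3 and 11.4 do not contradict 8.4.** Strictly, they are silent on study status. That silence still leaves staff without one rule.

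**Conclusion.** The concern holds. As written, the protocol has staff ask participants to leave the study for a reason tied to the primary outcome, does not secure their later assessments, and analyses the remainder as if the loss were explained by observed data. Under the assumed shares the bias is modest: 0.015 to 0.042 SD at ρ = 0.9 and up to 0.075 SD at ρ = 0.5. It would be larger if people left before T2. It favours the intervention if more treated than control participants leave this way, vanishes if the shares are equal, and reverses if more controls leave. Confidence in the mechanism is high. Confidence in direction and size is moderate, because the protocol gives neither rates nor their split by arm. It should be changed because the bias is avoidable at almost no cost.

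**What to change.** In Section 8.4, replace the instruction to leave the study with wording such as: *the participant stops the study intervention, if receiving it, and is advised to contact the general practitioner; T2 to T4 outcome assessments continue if the participant agrees; this applies in the same way in both arms.* In Sections 9.3 and 11.4, add a cross-reference to 8.4 for the participant's status in the study.

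Clinical triggers and referral actions stay as they are, and participants remain free to withdraw fully at their own wish.

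The cost is one sentence and two cross-references. No instrument, visit or sample size changes: T2 to T4 are already planned for everyone, mostly as online questionnaires, and N stays at 212.
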